4.2.2. Patient Exclusion Criteria

The presence of any of the following will exclude a patient from study enrollment:

1. Current enrollment in another interventional clinical study
2. Diagnosis of acute promyelocytic leukemia or BCR-ABL-positive leukaemia
3. Currently active second malignancy, except for adequately treated basal or squamous cell skin cancer and/or cone biopsied in situ carcinoma of the cervix uteri and/or superficial bladder cancer.
4. Patients with known leukemia involvement of CNS
5. Hematopoietic stem cell transplantation (HSCT) within 3 months of treatment starts and/or persistent non-hematologic toxicities of Grade ≥ 2 related to the transplant
6. Active acute or chronic graft versus host disease (GVHD) requiring immunosuppressive treatment

Statistical Analysis Plan

7. Patients with QTcF interval ≥ 480 milliseconds or with risk factors for torsade de pointes (e.g., uncontrolled heart failure, uncontrolled hypokalemia, history of prolonged QTc interval or family history of long QT syndrome). For patients receiving treatment with concomitant medications known to prolong the QTc interval, replacement with another treatment needs to be considered. If replacement or discontinuation is not clinically feasible, a careful risk/benefit evaluation should be performed prior to enrollment.
8. Pregnancy. All female patients with reproductive potential must have a negative pregnancy test (serum or urine) within the screening period prior to start of study drug.
9. Breast-feeding or planning to breast feed during the study or within 3 months after study treatment.
10. Known hypersensitivity to any of the components of the NMS-03592088 drug product.
11. Any of the following in the previous 6 months: myocardial infarction, unstable angina, coronary/peripheral artery bypass graft, symptomatic congestive heart failure, cerebrovascular accident or transient ischemic attack, pulmonary embolism, deep vein thrombosis
12. Known active, life threatening or clinically significant uncontrolled systemic infection.
13. Known human immunodeficiency virus (HIV) or acquired immunodeficiency syndrome (AIDS)-related illness
14. Active Hepatitis B Virus (HBV) or Hepatitis C Virus (HCV) C infection.
15. Known active gastrointestinal disease (e.g., Crohn's disease, ulcerative colitis, or short gut syndrome) or other malabsorption syndromes that would impact on drug absorption.
For US only: Known active gastrointestinal disease (e.g., Crohn's disease, ulcerative colitis, or short gut syndrome) or other malabsorption syndromes or gastric/intestinal resection that would impact on drug absorption.
16. Known active gastrointestinal ulcer
17. Other severe acute or chronic medical or psychiatric condition or laboratory abnormality that may increase the risk associated with study participation or study drug administration or may interfere with the interpretation of study results and, in the judgment of the Investigator, would make the patient inappropriate for entry into this study or could compromise protocol objectives in the opinion of the Investigator and/or the Sponsor.
18. Known diagnosis of myasthenia gravis

For France and US:

19. Concomitant anticoagulant use that is not already stabilized therapeutically
20. Subjects under legal protection or unable to express their consent; subjects deprived of liberty; subjects who are not members or not beneficiaries of a social security scheme.

For US only:

21. Signs or symptoms of myasthenia gravis or stroke during screening
22. Patients with myasthenia gravis specific autoantibodies (must be negative for anti-acetylcholine receptor or anti-MuSK at screening for entry) or any known history of MG autoantibodies at screening window
23. Concomitant medications with the potential to cause de novo myasthenia gravis, worsening of myasthenia gravis or cause myasthenia gravis-like symptoms as in <https://myasthenia-gravis.com/clinical/drugs-vaccines-to-avoid>.

Statistical Analysis Plan

24. Uncontrolled hypertension, atrial fibrillation or flutter, ventricular arrhythmia or receiving treatment for cardiac rhythm disorder or diabetes that is not adequately controlled

4.3. Sample Size

[REDACTED]

[REDACTED]

[REDACTED]

[REDACTED]

Phase II (For EU)

[REDACTED]

[REDACTED] In total, a sample size of approximately 180 pts is expected for the whole study.

[REDACTED]

[REDACTED]

[REDACTED]	[REDACTED]	[REDACTED]	[REDACTED]	[REDACTED]	[REDACTED]
[REDACTED]	[REDACTED]	[REDACTED]	[REDACTED]	[REDACTED]	[REDACTED]
[REDACTED]	[REDACTED]	[REDACTED]	[REDACTED]	[REDACTED]	[REDACTED]
[REDACTED]	[REDACTED]	[REDACTED]	[REDACTED]	[REDACTED]	[REDACTED]
[REDACTED]	[REDACTED]	[REDACTED]	[REDACTED]	[REDACTED]	[REDACTED]
[REDACTED]	[REDACTED]	[REDACTED]	[REDACTED]	[REDACTED]	[REDACTED]
[REDACTED]	[REDACTED]	[REDACTED]	[REDACTED]	[REDACTED]	[REDACTED]
[REDACTED]	[REDACTED]	[REDACTED]	[REDACTED]	[REDACTED]	[REDACTED]
[REDACTED]	[REDACTED]	[REDACTED]	[REDACTED]	[REDACTED]	[REDACTED]
[REDACTED]	[REDACTED]	[REDACTED]	[REDACTED]	[REDACTED]	[REDACTED]

[REDACTED]

4.4. Treatment Allocation and Blinding

Statistical Analysis Plan

Not applicable.

5. OVERVIEW OF PLANNED ANALYSES**5.1. Independent Data Monitoring Committee (IDMC)**

An Official Independent Data Monitoring Committee is not foreseen. Regular teleconferences will be organized between the Investigators and the Sponsor to strictly review all relevant safety issue (e.g., grade 3-4 clinical and laboratory events, drug-related Serious Adverse Events and Deaths) and take decision on the dose escalation, where applicable.

5.2. Planned Schedule of Interim Analyses**5.2.1. Futility Analysis**

[REDACTED]

[REDACTED]

5.2.2. Safety Analysis

[REDACTED]

[REDACTED]

[REDACTED]

Statistical Analysis Plan

All final planned analyses identified in the protocol and in this SAP will be performed only after the last patient has completed the final visit, including follow up, and all relevant study data have been processed and integrated into the analysis datasets and the database has been cleaned and locked. Any post-hoc exploratory analyses performed to provide support for planned analyses but not identified in this SAP will be documented and reported in appendices to the CSR and clearly identified as unplanned analyses in the text of the CSR.

The mock-ups tables, listings and graphs for reporting purpose are described in a separate document.

6. CHANGES IN THE PLANNED ANALYSIS

Not applicable.

7. ANALYSIS POPULATIONS

As stated in the CT Protocol, for the purpose of the analysis, the following patient populations are defined: Enrolled Patients, Treated Patients, Patients evaluable for determination of DLT (by dose schedule and dose level) and patients evaluable for efficacy analysis (efficacy dataset).

Enrolled Patients: This population will include all patients who are enrolled in the clinical study, regardless of whether patients receive treatment or not. This population will be evaluated in the analysis of patients' disposition.

Treated Patients: The treated patient population consists of all enrolled patients who actually receive at least one treatment administration. This population will be evaluated in the analysis of patient disposition, baseline characteristics, treatment exposure, efficacy and safety.

Patients evaluable for determination of DLT (by dose schedule and dose level): for each schedule and dose level tested, this population includes all patients enrolled in dose escalation part who receive at least 70% of drug in the first cycle, unless the reason for non-compliance is drug-related toxicity, and for whom a DLT assessment is available within the DLT window. In case the patient does not fulfill one or more of the aforementioned criteria, he/she will be replaced.

Patients evaluable for efficacy analysis (efficacy dataset): This is the patient population which consists of all enrolled patients in the Phase II part who are treated at the RP2D, have ≥ 1 on-treatment hematologic assessment(s) (i.e., they must have adequate bone marrow response evaluation). Patients who experience early death or withdrew prior to response assessment, or had technically suboptimal bone marrow sample precluding assessment, are non-evaluable for response and are excluded from the efficacy dataset. For cohort 1 and 2, only the subset of patients with FLT3-ITD mutation and no D835 mutation based on the central test will be included in this population.

For US only:

Patients evaluable for efficacy analysis (efficacy dataset): efficacy datasets will be defined by dose level, patients receiving at least 75% of treatment at first cycle, have at least one or more on-treatment hematologic assessment(s) (i.e., they must have adequate bone marrow response evaluation), relative to ELN criteria, must have adequate baseline. Note: Patients who are not evaluable for efficacy due to early death, inadequate bone marrow sample, or withdrawal from the study prior to evaluation should be considered failures rather than non-evaluable

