
considerations among other features.
 
This dose may be the dose recommended for further investigations.
 
Phase I: Dose-Expansion and Backfill
 
For each schedule, once the MTD or MAD is identified and safety and PK data have been reviewed by the Investigators and the Sponsor and are considered adequate, a maximum of 10 additional patients will be enrolled and treated at the MTD or MAD to further characterize the safety and tolerability profile of NMS-03592088 and to better define the recommended dose and the schedule for the Phase II portion of the study. In the dose expansion and in the backfill cohorts the Sponsor may restrict the enrollment to AML FLT3 positive patients and/or to patients with specific prior lines or therapies. Up to 4 backfill cohorts of up to 14 patients each may enroll at doses and schedules no higher than RP2D or exposure equivalent and may include the following: 1) first cycle at reduced dose/exposure relative to RP2D to collect additional PK, matched PK/ECG for standard E14 update exposure/QTc, biomarkers, and anti-cancer activity followed by subsequent cycle up to RP2D or exposure equivalent; 2) food effect with first cycle no higher than RP2D or equivalent exposure followed by subsequent cycle with standard meal on day 1 of cycle 2 only. The exposure cap described above will be followed.
 
Phase II: Expansion Cohorts
 
Once the RP2D and schedule of NMS-03592088 have been selected, the exploratory Phase II portion of the study will be opened for enrollment and will consist of two parallel cohorts:
 
 
- Cohort 1 (40 patients with a futility analysis at 10 patients): patients with AML FLT3 Internal Tandem Duplication (ITD) mutation as assessed by central laboratory, who have failed standard of care including venetoclax and gilteritinib based therapies. Dose and schedule will be within the defined exposure cap rule (see above). The enrollment in this cohort may be restricted to patients with specific prior lines/therapies and/or mutations, based on Sponsor decision.
 
- Cohort 2 (40 patients with a futility analysis at 10 patients): patients with AML FLT3 Internal Tandem Duplication (ITD) mutation as assessed by central laboratory, who have failed standard of care. Dose and schedule will be within the defined exposure cap rule (see above). The cohort may be restricted to patients with specific prior lines/therapies and/or mutations, based on Sponsor decision.
 
 
The Sponsor will control the patient assignment to cohorts and may stop or pause cohorts in any phase or part of the study based on safety, efficacy or strategic reasons (note: while finalizing this document, the Sponsor has temporarily restricted cohort 2 to include patients with AML FLT3 Internal Tandem Duplication (ITD) mutation (as assessed by central laboratory) who have failed standard of care including intensive induction chemotherapy in first line of treatment and Gilteritinib based therapy in any line of prior treatments)
 
Dose modification: See Section 9.2.3.
 
Treatment Duration
 
Patients may continue on study treatment until disease progression, unacceptable toxicity, investigator decision, withdrawal of consent by the patient or other discontinuation criteria detailed in Section 10 are met.
 
Sample Size Determination
 
CCI
	

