**Table 1 Estimated 95% Confidence Intervals for Assumed CRc Rates at Interim Analysis**

Number of Treated Patients	Number of Patients Who Achieve Response	Observed CRc Rate (%)	Lower Bound Exact 95% CI (%)	Upper Bound Exact 95% CI (%)	Half-Width of CI (%)
10	1	10.00	0.25	44.50	22.13
10	2	20.00	2.52	55.61	26.55
10	3	30.00	6.67	65.25	29.29

Overall, considering both parts of the study, a maximum of approximately 180 patients is expected.

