## 12.2. Definition of Analyzed Study Populations

For the purpose of the analysis, the following patient populations are defined and the endpoints, to be analyzed in these populations, are specified:

- *Enrolled Patients*: This population will include all patients who are enrolled in the clinical study, regardless of whether patients receive treatment or not. This population will be evaluated in the analysis of patients' disposition.
- *Treated Patients*: The treated patient population consists of all enrolled patients who actually receive at least one treatment administration. This population will be evaluated in the analysis of patient disposition, baseline characteristics, treatment exposure, efficacy and safety.
- *Patients evaluable for determination of DLT (by dose schedule and dose level)*: for each schedule and dose level tested, this population includes all patients enrolled in dose escalation part who receive at least 70% of drug in the first cycle, unless the reason for non compliance is drug-related toxicity, and for whom a DLT assessment is available within the DLT window. In case the patient does not fulfill one or more of the aforementioned criteria, he/she will be replaced.
- *Patients evaluable for efficacy analysis (efficacy dataset)*: This is the patient population which consists of all enrolled patients in the Phase II part who are treated at the RP2D, have  $\geq 1$  on-treatment hematologic assessment(s) (i.e. they must have adequate bone marrow response evaluation). Patients who experience early death or withdrew prior to response assessment, or had technically suboptimal bone marrow sample precluding assessment, are non-evaluable for response and are excluded from the efficacy dataset. For cohort 1 and 2, only the subset of patients with FLT3-ITD mutation and no D835 and I836 mutations based on the central test will be included in this population.
- *Patients evaluable for PK analysis*: treated patients will be considered evaluable if they have sufficient baseline and on-study sampled material to provide interpretable results.

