2. PURPOSE OF THE STATISTICAL ANALYSIS PLAN

This Statistical Analysis Plan (SAP) describes the planned statistical analyses and reporting for MKIA-088-001 Clinical Trial (CT). All analyses take origin from the specifications in the statistical section of the CT Protocol.

Of note, this SAP does not cover the pharmacokinetic (PK) data analyses and the exploratory pharmacodynamic (PD) and ECGs analyses described in the CT Protocol.

The structure and content of this SAP provide sufficient detail to guarantee compliance with the requirements identified by the International Conference on Harmonization of Technical Requirements for Registration of Pharmaceuticals for Human Use (ICH): E9 Guidance on Statistical Principles in Clinical Trials and Integrated Addendum to E9(R1) [1].

The planned analyses identified in this SAP will be included in future abstracts, presentations and manuscripts and may also support other documents, e.g., Development Safety Update Report (DSUR) preparation. Exploratory analyses not necessarily identified in this SAP may be performed to support planned analyses. Any post-hoc or unplanned analyses not specified in this SAP will be clearly identified as such in the Clinical Study Report (CSR) and manuscripts for publication.

The following documents were reviewed when preparing this SAP:

- CT EU Consolidated Protocol version 8.0 (18-Oct-2023) and CT Protocol version 7.5 (18 Aug 2023) for US for CT MKIA-088-001.
- CT Casebook versions up to the last approved 3.14 (06-Nov- 2023) for CT MKIA-088-001
- E9 - Statistical Principles for Clinical Trials [Integrated Addendum to E9(R1) [1]
- E6(R2) - Guidance on Good Clinical Practice [Integrated Addendum to E6(R1) [1]
- E3 - Guidance on Structure and Content of Clinical Study Reports [1].
- Applicable NMS procedural documents

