For Europe countries, up to 4 backfill cohorts of up to 10 patients each may enroll at doses and schedules no higher than RP2D or exposure equivalent and may include the following: 1) first cycle at reduced dose/exposure relative to RP2D to collect additional PK, matched PK/ECG for standard E14 update exposure/QTc, biomarkers, and anti-cancer activity followed by subsequent cycle up to RP2D or exposure equivalent; 2) food effect with first cycle no higher than RP2D or exposure equivalent followed by subsequent cycle with standard meal on day 1 of cycle 2 only. After day 1 of cycle 2, patients will continue treatment in fasting condition.

In Phase II, the following cohorts will be studied in parallel:

Cohort 1 (40 patients with a futility analysis at 10 patients): patients with AML FLT3 Internal Tandem Duplication (ITD) mutation as assessed by central laboratory, who have failed standard of care including venetoclax and gilteritinib based therapies. Dose and schedule will be within the defined exposure cap rule defined above. The enrollment in this cohort may be restricted to patients with specific prior lines/therapies and/or mutations, based on Sponsor decision.

Cohort 2 (40 patients with a futility analysis at 10 patients): patients with AML FLT3 Internal Tandem Duplication (ITD) mutation as assessed by central laboratory, who have failed standard of care. Dose and schedule will be within the defined exposure cap rule defined above. The cohort may be restricted to patients with specific prior lines/therapies and/or mutations, based on Sponsor decision.

The Sponsor will control the patient assignment to cohorts and may terminate any cohort in any phase at any time during the study based on safety, PK or strategic reasons.

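### SAP v3.0 cites protocol v8.0/v7.5 rather than v9, leaves I836 out of the efficacy-dataset rule, and gives a backfill ceiling 16 patients lower than the protocol's

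*SAP*

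**What the plan says.** **Source versions.** SAP section 2 lists as its basis "CT EU Consolidated Protocol version 8.0 (18-Oct-2023) and CT Protocol version 7.5 (18 Aug 2023) for US for CT MKIA-088-001". SAP section 2.1 treats these as the approved versions in force. The SAP's version history dates v3.0 to 28-Mar-2024; the protocol supplied is version 9 of 28 February 2024. SAP section 6, on changes to the planned analysis, is marked not applicable.

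**Efficacy dataset, cohorts 1 and 2.** SAP section 7 introduces its populations as those of the protocol and then states that "only the subset of patients with FLT3-ITD mutation and no D835 mutation based on the central test will be included in this population". Protocol 12.2 instead keeps "only the subset of patients with FLT3-ITD mutation and no D835 and I836 mutations based on the central test". Protocol inclusion criterion 2 makes patients with either mutation ineligible, but lets those with very rapidly proliferating disease enter on a local test when they cannot wait for the central result.

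**Backfill and total.** SAP 4.1, for European countries, allows "up to 4 backfill cohorts of up to 10 patients each". The protocol synopsis, under dose expansion and backfill, says "Up to 4 backfill cohorts of up to 14 patients each". On the overall number, the synopsis says "a maximum of approximately 180 patients is expected" and SAP 4.3 says "a sample size of approximately 180 pts is expected for the whole study".

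**The concern.** A SAP that says it repeats the protocol's populations and declares no departures should give the same analysis set when programmed. Here it does not: a program written from SAP section 7 keeps a patient whom protocol 12.2 removes. The central-test filter matters because local-test enrolment is allowed. It is the step that takes out a patient whose excluded mutation shows only on the central result, and the SAP's filter checks one of the two excluded mutations.

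At stake is agreement between the two documents on who counts in the Phase II response rate. The synopsis lets a cohort continue if at least one CR or CRi is seen among at least 10 evaluable patients. If evaluable there means the efficacy dataset, which the visible text does not confirm, a sole responder who proved I836-positive would count under the SAP and not under the protocol.

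The backfill figures raise a separate question. The ceiling differs by 16 while the overall total is the same, so it is unclear which ceiling about 180 was meant to cover.

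**Working it through.** **1. Dates.** From 28-Feb-2024 (protocol v9) to 28-Mar-2024 (SAP v3.0) is 29 days. The SAP's source list does not include v9.

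**2. The mutation rule, case by case** (FLT3-ITD positive on the central test, all other conditions met):

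| Central result | Protocol 12.2 | SAP section 7 |
|---|---|---|
| D835 negative, I836 negative | in | in |
| D835 positive | out | out |
| D835 negative, I836 positive | out | **in** |

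The rules part only in the last row. SAP 9.3 tabulates I836 status at baseline, so the data needed to apply the protocol's rule are available.

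**3. Size of the effect.** The documents give neither an expected number of I836-positive patients nor a usable response count, so these inputs are assumptions: n = 40 in the dataset under the SAP rule, r = 8 responders, k patients removed by the protocol rule.

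- SAP rule: 8/40 = 20.0% (exact 95% CI 9.05% to 35.65%).
- k = 1: 8/39 = 20.5% if a non-responder, (8 − 1)/39 = 17.9% if a responder.
- k = 2: 8/38 = 21.1% if both are non-responders, 6/38 = 15.8% if both are responders.
- k = 4: 8/36 = 22.2% if all are non-responders, 4/36 = 11.1% if all are responders.

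Removing one responder lowers the rate by (n − r)/[n(n − 1)]; removing one non-responder raises it by r/[n(n − 1)]. At r = 8 these are 32/1560 = 2.1 points and 8/1560 = 0.5 points. The most that one responder can move a 40-patient rate is 39/1560 = 2.5 points, at r = 1.

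**4. Backfill and the total.** Protocol 4 × 14 = 56; SAP 4 × 10 = 40; difference 16, or 16/180 = 8.9% of the total.

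The figure of about 180 cannot be rebuilt, because the Phase I sample-size text is redacted in both documents. What can be checked is the room left for dose escalation, E, if 180 is a ceiling. Phase II is 40 + 40 = 80. Dose expansion is at most 10 per schedule, so up to 20 over two schedules.

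| Expansion used | E with backfill 56 (protocol) | E with backfill 40 (SAP) |
|---|---|---|
| 20 | 180 − 80 − 20 − 56 = 24 | 180 − 80 − 20 − 40 = 40 |
| 10 | 34 | 50 |
| 0 | 44 | 60 |

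Even with every cap filled, any E of 24 or fewer satisfies both documents.

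**The case against.** **The SAP may have been right when it was written.** The date on v9 is a document date, not an approval date, and protocol 16.1 requires ethics approval before an amendment is implemented. Versions 8.0 and 7.5 may still have been the approved ones, and section 6 may be accurate against them. This stands as an explanation, and it limits what can be said about cause: those versions are not supplied, so the I836 omission could be a drafting slip unrelated to version. It does not remove the mismatch with v9.

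**Eligibility already bars I836-positive patients.** True, so the gap is narrow. The realistic route is a local-test enrolee later found positive centrally, or an eligibility violation. SAP 9.2 also lists ineligible patients individually, so such a case would be seen. But a listing does not take the patient out of the dataset.

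**It may not be the primary set.** A reader might infer that the primary CRc analysis is affected. The efficacy analysis text is redacted in both documents, and Treated Patients is also named for efficacy, so this cannot be confirmed.

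**The caps are upper limits.** A reader might infer that 180 cannot fit both documents, or that the true maximum is 180 + 16 = 196. Neither follows. The backfill and expansion numbers are ceilings, the total is approximate, and the sponsor may stop or pause cohorts. The 196 arises only by carrying the SAP residual of 40 escalation patients into the protocol's sum, and neither document visibly states that number. Only if 180 were an exact sum of all caps with one escalation number would the two conflict. The SAP's ceiling is also worded for European countries while the synopsis sets no such limit, so the two caps may not cover the same sites.

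**Conclusion.** The point holds as a document-alignment defect with one substantive part. SAP section 7 states a mutation filter that differs from protocol 12.2 and inclusion criterion 2, and following it would keep a centrally I836-positive patient whom the protocol removes. The number affected is probably small. At the assumed 8/40, one such patient changes the rate by 0.5 points (non-responder) or 2.1 points (responder), and by no more than 2.5 points at any response count for a responder.

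The backfill ceilings differ by 16 (40 against 56) and should be reconciled. This does not show that about 180 is wrong in either document, since an escalation of up to 24 fits both with all caps filled.

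The version citation is out of step with v9. Whether that caused the two differences cannot be established from the documents supplied.

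**What to change.** - **SAP section 7:** change the cohort 1 and 2 condition to 'no D835 and no I836 mutation' on the central test, to match protocol 12.2.
- **SAP 4.1:** align the backfill ceiling with the governing protocol and say which countries it covers.
- **SAP section 2:** cite v9, or state why v8.0/v7.5 governs. Then revisit section 6 so that any remaining departure is declared.
- **Total:** check that about 180 still covers the larger backfill ceiling once the escalation number, which the sponsor holds, is put in. Restate it only if it does not. Showing the components would settle the question.

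The cost is a SAP revision before the final analysis. No new data are needed, because I836 status is already tabulated at baseline.
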